13 SUMMARY OF PLANNED EFFICACY ANALYSES

At the BDRM it might be decided not to perform any analyses for the PP set (depending on the number of patients to be excluded from the ITT set) and to add analyses for sensitivity and / or additional subgroups.

Type of endpoint	Endpoint	Analysis set	Stratification	Test	Other feature	Relevance
primary	OS	ITT	ECOG, RISK (randomization)	Log-rank	none	Primary analysis for this endpoint
primary	OS	ITT	ECOG (Day 1 Cycle 1), RISK (centralized)	Log-rank	none	sensitivity
primary	OS	ITT	none	Log-rank	none	sensitivity
primary	OS	ITT	ECOG, RISK (randomization)	Cox PH	none	sensitivity
primary	OS	ITT	ECOG, RISK (randomization)	Log-rank	Censor at time of new therapy	sensitivity
primary	OS	PP	ECOG, RISK (randomization)	Log-rank	none	Secondary set
primary	OS	ITT	ECOG, RISK (randomization) + other factors	Cox PH	none	Exploratory Factors and related levels to be decided at BDRM
First secondary	CR	ITT	ECOG, RISK (randomization)	CMH	none	Primary analysis for this endpoint
First secondary	CR	EE-1	ECOG, RISK (randomization)	CMH	none	Secondary set
First secondary	CR	ITT	none	LRT	none	sensitivity
First secondary	CR	EE-1	none	LRT	none	Sensitivity on secondary set

First secondary	CR	ITT	ECOG, RISK (randomization) + other factors	Logistic regression	none	Exploratory Factors and related levels to be decided at BDRM
Second secondary	Transfusion independence	ITT	ECOG, RISK (randomization)	CMH	none	Primary analysis for this endpoint
Third secondary	CR _{M RD} -	ITT	ECOG, RISK (randomization)	CMH	none	Primary analysis for this endpoint
Third secondary	CR _{M RD} -	EE-1	ECOG, RISK (randomization)	CMH	none	Secondary set
Fourth secondary	CRc	ITT-2	ECOG, RISK (randomization)	CMH	none	Primary analysis for this endpoint
Fourth secondary	CRc	EE-2	ECOG, RISK (randomization)	CMH	none	Sensitivity on secondary set
Explorative	cCR	ITT	ECOG, RISK (randomization)	CMH	none	Primary analysis for this endpoint
Explorative	cCR	EE-1	ECOG, RISK (randomization)	CMH	none	Secondary set
Explorative	BR	ITT	none	none	none	Primary analysis for this endpoint
Explorative	BR	EE-1	none	none	none	Secondary analysis for this endpoint
Explorative	RFS	ITT	ECOG, RISK (randomization)	Log-rank	none	Primary analysis for this endpoint
Explorative	RFS	ITT	ECOG, RISK (randomization)	Log-rank	Censor at time of new therapy	sensitivity
Explorative	PFS	ITT	ECOG, RISK (randomization)	Log-rank	none	Primary analysis for this endpoint

Explorative	PFS	ITT	ECOG, RISK (randomization)	Log-rank	Censor at time of new therapy	sensitivity
Explorative	Duration of CR	ITT	ECOG, RISK (randomization)	Log-rank	Censor at time of new therapy	Primary analysis for this endpoint
Explorative	Duration of cCR	ITT	ECOG, RISK (randomization)	Log-rank	Censor at time of new therapy	Primary analysis for this endpoint
Explorative	Time to CR	ITT	ECOG, RISK (randomization)	Long-rank	none	Primary analysis for this endpoint
Explorative	CR within 6 cycles	ITT	ECOG, RISK (randomization)	CMH	none	Primary analysis for this endpoint
Subgroups	OS, CR, CRc CR _{MRD} - Transfusion independence	ITT as relevant (only the primary set)	ECOG, RISK (randomization) if feasible Otherwise unstratified	Log-rank or CMH or Logistic regression (as relevant)	Features used in the main analysis of each endpoint	Not Applicable

14 SORTING OF LISTINGS

General sorting will include strata (as randomized: cytogenetic risk Intermediate/Unfavorable, ECOG performance status 0-1/2), treatment group (Pracinostat+AZA / Placebo+AZA) and patient number.

Sorting of unscheduled visits should be managed by properly assigning to one cycle (then sorting by date).

Listings will be sorted as follows:

Listing	Sorted by
Listing Shell A1 Disposition of patients	GENERAL
Listing Shell A2 All protocol deviations	GENERAL
Listing Shell A3 Stratification factors	GENERAL
Listing Shell B1 Demographic characteristics	GENERAL
Listing Shell B2 Current Cancer History	GENERAL

Listing Shell B3 Prior Hematologic Disorder Antecedent to AML	GENERAL
Listing Shell B4 Left Ventricular Ejection Fraction (LVEF)	GENERAL
Listing Shell B5 Pulmonary Function Test	GENERAL
Listing Shell B6 Bone Marrow Aspirate/Biopsy	GENERAL, Cycle
Listing Shell B7 Classic Cytogenetics	GENERAL, Cycle
Listing Shell B8 Cytogenetics (FISH) (optional)	GENERAL, Cycle
Listing Shell B9 Molecular Analysis (optional)	GENERAL, Cycle
Listing Shell B10 Medical History (excluding AML specific terms)	GENERAL, SOC, PT
Listing Shell B11 Prior and Concomitant medication	prior/concomitant, GENERAL, PT, start date
Listing Shell B12 Prior and Concomitant Procedures	prior/concomitant, GENERAL, procedure, start date
Listing Shell B13 Therapy for Antecedent Hematological Disorder	GENERAL, medication, start date
Listing Shell B14 New AML treatment	GENERAL, treatment, start date
Listing Shell B15 Prior or Concomitant Medication regarded as New AML treatment	GENERAL, PT
Listing Shell E1 Overall survival	GENERAL
Listing Shell E2 Overall survival – censoring due to new interceding therapies	GENERAL
Listing Shell E3 Relapse Free Survival	GENERAL
Listing Shell E4 Relapse Free Survival – censoring due to new interceding therapies	GENERAL
Listing Shell E5 Progression Free Survival	GENERAL
Listing Shell E6 Progression Free Survival – censoring due to new interceding therapies	GENERAL
Listing Shell E7 Morphologic Complete Remission	GENERAL

Listing Shell E8 Composite Complete Remission (cCR)	GENERAL
Listing Shell E9 Cytogenic Complete Remission (CRc) only for subjects achieving CR	GENERAL
Listing Shell E10 MRD specific parameters	GENERAL, Visit, Date
Listing Shell E11 Duration of Morphologic Complete Remission	GENERAL
Listing Shell E12 Duration of Composite Complete Remission	GENERAL
Listing Shell E13 Transfusion Independence	GENERAL, Visit, Date, kind of transfusion
Listing Shell E14 Summary of efficacy results per patient and cycle	GENERAL, cycle, date of assessment, date BM/Blood
Listing Shell E15 EORTC QLQ C30	GENERAL, Visit, Type of scale, Scale, Question
Listing Shell E16 Compliance to Pracinostat/ Placebo	GENERAL, Cycle, Date dose taken
Listing Shell E17 Compliance to AZA	GENERAL, Cycle, Date dose taken
Listing Shell E18 Follow-up visits	GENERAL, Visit date
Listing Shell E19 Patients with drug holidays	GENERAL
Listing Shell F1 Exposure to Pracinostat/Placebo	GENERAL, Cycle, Week, Day
Listing Shell F2 Exposure to Azacitidine	GENERAL, Cycle, Week, Day
Listing Shell F3 Exposure to Study Drug – cumulative doses	GENERAL
Listing Shell F4 Exposure to Study Drug – cumulative number of administrations	GENERAL, Cycle
Listing Shell F5 Exposure to Study Drug – interruptions and discontinuations	GENERAL, Cycle
Listing Shell F6 Pre Treatment adverse events	GENERAL, PT, Start date
Listing Shell F7 Treatment emergent adverse events	GENERAL, PT, Start date
Listing Shell F8 Post treatment adverse events	GENERAL, PT, Start date

Listing Shell F9 Adverse events – initial and follow-up records	GENERAL, PT, Start date, Initial/Follow-up #1 to Last
Listing Shell F10 Serious Adverse Events	GENERAL, PT, Start date
Listing Shell F11 Serious Adverse Events leading to death	GENERAL, PT, Start date
Listing Shell F12 Adverse Events leading to any study treatment discontinuation	GENERAL, PT, Start date
Listing Shell F13 Adverse Events of Special Interest	GENERAL, PT, Start date
Listing Shell F14 Deaths	GENERAL
Listing Shell F15 Vital Signs	GENERAL, Visit, Parameter
Listing Shell F16 Clinical safety laboratory – hematology panel (blood counts)	GENERAL, Parameter, Visit
Listing Shell F17 Clinical safety laboratory – hematology panel (serology and HIV)	GENERAL, Parameter, Visit
Listing Shell F18 Clinical safety laboratory - chemistry panel	GENERAL, Parameter, Visit
Listing Shell F19 Clinical safety laboratory - coagulation panel	GENERAL, Parameter, Visit
Listing Shell F20 ECG results	GENERAL, Parameter, Visit
Listing Shell F21 Physical exam	GENERAL, Parameter, Visit
Listing Shell F22 Unblinding by investigator	GENERAL, Parameter, Visit

15 GRADES ASSIGNED TO LABORATORY DATA

The following table reports the grades assigned to selected laboratory parameters (according to NCI CTCAE version 4.03).

	Grade 1	Grade 2	Grade 3	Grade 4
Albumin decreased	<LLN - 3 g/dL; <LLN - 30 g/L	<3 - 2 g/dL; <30 - 20 g/L	<2 g/dL; <20 g/L	missing
Alkaline Phosphatase increased	>ULN - 2.5 x ULN	>2.5 - 5.0 x ULN	>5.0 - 20.0 x ULN	>20.0 x ULN

Alanine aminotransferase (ALT) increased	>ULN - 3.0 x ULN	>3.0 - 5.0 x ULN	>5.0 - 20.0 x ULN	>20.0 x ULN
Activated partial thromboplastin time (APTT) prolonged	>ULN - 1.5 x ULN	>1.5 - 2.5 x ULN	>2.5 x ULN	missing
Aspartate aminotransferase (AST) increased	>ULN - 3.0 x ULN	>3.0 - 5.0 x ULN	>5.0 - 20.0 x ULN	>20.0 x ULN
Calcium increased	>ULN- 1.5 mmol/L	>1.5 -1.6 mmol/L	>1.6 -1.8 mmol/L	>1.8 mmol/L
Calcium decreased	<LLN - 1.0 mmol/L	<1.0 - 0.9 mmol/L	<0.9 - 0.8 mmol/L	<0.8 mmol/L
Creatinine increased	>ULN - 1.5 x ULN	>1.5 - 3.0 x ULN	>3.0 - 6.0 x ULN	>6.0 x ULN
Creatinine clearance decreased	<LLN – 60 ml/min/1.73 m2	59 – 30 ml/min/1.73 m2	29 – 15 ml/min/1.73 m2	<15 ml/min/1.73 m2
Fibrinogen decreased	<1.0 - 0.75 x LLN	<0.75 - 0.5 x LLN	<0.5 - 0.25 x LLN	<0.25 x LLN
Glucose increased	>ULN - 160 mg/dL (>ULN -8.9 mmol/L)	>160 - 250 mg/dL (>8.9 - 13.9 mmol/L)	>250 - 500 mg/dL (>13.9 - 27.8 mmol/L)	>500 mg/dL (>27.8 mmol/L)
Glucose decreased	<LLN - 55 mg/dL (<LLN -3.0 mmol/L)	<55 - 40 mg/dL (<3.0 - 2.2 mmol/L)	<40 - 30 mg/dL (<2.2 - 1.7 mmol/L)	<30 mg/dL (<1.7 mmol/L)
Hemoglobin decreased	<LLN - 10.0 g/dL (<LLN - 100 g/L)	<10.0 - 8.0 g/dL (<100 - 80g/L)	Hgb <8.0 g/dL (<80 g/L)	missing
INR increased	>1 - 1.5 x ULN	>1.5 - 2.5 x ULN	>2.5 x ULN	missing
Lymphocyte count decreased	<LLN - 800/mm3 (<LLN - 0.8 x 10e9 /L)	<800 - 500/mm3 (<0.8 - 0.5 x 10e9 /L)	<500 - 200/mm3 (<0.5 - 0.2 x 10e9 /L)	<200/mm3 (<0.2 x 10e9 /L)
Lymphocyte count increased	missing	>4000/mm3 - 20,000/mm3	>20,000/mm3	missing

Magnesium increased	>ULN - 3.0 mg/dL (>ULN - 1.23 mmol/L)	missing	>3.0 - 8.0 mg/dL (>1.23 - 3.30 mmol/L)	>8.0 mg/dL (>3.30 mmol/L)
Magnesium decreased	<LLN - 1.2 mg/dL (<LLN - 0.5 mmol/L)	<1.2 - 0.9 mg/dL (<0.5 - 0.4 mmol/L)	<0.9 - 0.7 mg/dL (<0.4 - 0.3 mmol/L)	<0.7 mg/dL (<0.3 mmol/L)
Neutrophil count decreased	<LLN - 1500/mm3 (<LLN - 1.5 x 10e9 /L)	<1500 - 1000/mm3 (<1.5 - 1.0 x 10e9 /L)	<1000 - 500/mm3 (<1.0 - 0.5 x 10e9 /L)	<500/mm3 (<0.5 x 10e9 /L)
Phosphorus decreased	<LLN - 2.5 mg/dL (<LLN - 0.8 mmol/L)	<2.5 - 2.0 mg/dL (<0.8 - 0.6 mmol/L)	<2.0 - 1.0 mg/dL (<0.6 - 0.3 mmol/L)	<1.0 mg/dL (<0.3 mmol/L)
Platelet count decreased	<LLN - 75,000/mm3 (<LLN - 75.0 x 10e9 /L)	<75,000 - 50,000/mm3 (<75.0-50.0 x 10e9 /L)	<50,000 - 25,000/mm3 (<50.0-25.0 x 10e9 /L)	<25,000/mm3 (<25.0 x 10e9 /L)
Potassium increased	>ULN - 5.5 mmol/L	>5.5 - 6.0 mmol/L	>6.0 - 7.0 mmol/L	>7.0 mmol/L
Potassium decreased	<LLN - 3.0 mmol/L	missing	<3.0 - 2.5 mmol/L	<2.5 mmol/L
Sodium increased	>ULN - 150 mmol/L	>150 - 155 mmol/L	>155 - 160 mmol/L	>160 mmol/L
Sodium decreased	<LLN - 130 mmol/L	missing	<130 - 120 mmol/L	<120 mmol/L
Total bilirubin increased	>ULN - 1.5 x ULN	>1.5 - 3.0 x ULN	>3.0 - 10.0 x ULN	>10.0 x ULN
Uric acid increased	>ULN - 10 mg/dL (0.59 mmol/L)	missing	missing	>10 mg/dL (>0.59 mmol/L)
White blood cell decreased	<LLN - 3000/mm3 (<LLN - 3.0 x 10e9 /L)	<3000 - 2000/mm3 (<3.0 - 2.0 x 10e9 /L)	<2000 - 1000/mm3 (<2.0 - 1.0 x 10e9 /L)	<1000/mm3 (<1.0 x 10e9 /L)

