Prior to pracinostat administration, hypokalemia, hypophosphatemia and hypomagnesaemia should be corrected and consideration should be given to monitoring potassium and magnesium in symptomatic patients (e.g., patients with nausea, vomiting, diarrhea, fluid imbalance, or cardiac symptoms). Concomitant medications with a known risk of prolonging the QT interval and/or causing Torsades de Pointes are prohibited. In addition, caution should be taken when using concomitant medications with a possible or conditional risk of prolonging the QT interval and/or causing Torsades de Pointes. Medications with a possible or conditional risk may be used at the discretion of the Investigator ([Appendix I](#)).

Subjects requiring any medications that have the potential to alter serum electrolytes (e.g., diuretics) should be monitored closely for electrolyte abnormalities as these can contribute to the risk of QT prolongation and ventricular arrhythmias.

4.2.2.5 *Procreation*

Among the observed adverse effects of pracinostat in 28-day repeated oral dose toxicity studies conducted in CD1 mice, also testicular effects were reported ([Investigator's Brochure](#)). Investigators should advise male patients to consider cryopreservation of semen.

4.2.2.6 *Phototoxicity*

Pracinostat was evaluated for phototoxicity in murine fibroblasts, using the neutral red uptake assay, up to a concentration of 100 µg/mL. The calculated IC₅₀ value after

exposure with and without irradiation was 22 and 12 µg/mL, respectively. This resulted in a Photo Irritation Factor (PIF) of 0.54 and a Mean Photo effect of -0.004 leading to the classification ‘nonphototoxic’ (PRAN-17-39). No measures are therefore to be taken to minimize exposure to UV light.

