6.2.4 Laboratory Assessments

Blood samples will be collected at the relevant visits as indicated in Section 5.1 (i.e., Screening, Day 15 of Cycle 1, Day 1 of Cycle 2, between Day 21-26 of Cycle 2 and all subsequent cycles and End of Treatment Visit). All blood samples will be sent to the central laboratory for analysis (for details regarding processing and shipment please refer to the separate manual).

Females of childbearing potential will perform serum beta-hCG pregnancy tests at screening visit, Day 1 of Cycle 2, between Day 21 and Day 26 of Cycle 2 and all subsequent cycles and End of Treatment Visit. Pregnancy will be re-evaluated by urine pregnancy test (dipstick done locally at study site) predose on Day 1 of Cycle 1.

The following parameters will be analyzed for each sample:

Hematology panel: complete blood count (CBC): hematocrit, hemoglobin, erythrocytes (RBC), platelets, leukocytes (WBC) with differential (neutrophils, lymphocytes, basophils, eosinophils, monocytes and blasts).

HBV serology (HBsAg, antibody to HBsAg [anti-HBs], anti-HBc, HCV serology (anti-HCV) and HIV will be required only at screening.

HIV will be performed based on local regulation at local laboratory. HIV test already performed within 30 days prior to the ICF signature will be accepted as screening evaluation.

Blood chemistry panel: glucose, blood urea nitrogen/urea, creatinine, creatinine clearance (derived from blood creatinine value by Cockcroft formula), sodium, potassium, chloride, calcium, phosphorus, magnesium, bicarbonate /carbon dioxide (CO₂), alkaline phosphatase (ALP), alanine aminotransferase (ALT), aspartate aminotransferase (AST), total bilirubin, total protein, uric acid, albumin, and lactic acid dehydrogenase (LDH)

Coagulation panel: PT, INR, PTT, fibrinogen, D dimer

After review of the laboratory data, the Investigator must sign and date each laboratory report. The laboratory will provide normal reference ranges on the laboratory results report and will flag all abnormal values. The Investigator will assess the clinical relevance of values outside the normal range and repeat, if needed, any clinically significant abnormal laboratory test.

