9.4 CLINICAL LABORATORY EVALUATION ANALYSES

Clinical laboratory values (hematological panel, blood chemistry panel, and coagulation panel, as described in the clinical study protocol in section 6.2.4) will be analyzed.

Descriptive statistics will be provided for the clinical laboratory results for the SAF set by treatment cycle, as well as for the change from baseline (leukocytes differential counts expressed as percentage on leukocytes will only be listed). The baseline value is defined as the last non-missing value before the initial administration of study treatment. In addition, change from baseline will be summarized for the maximum and minimum post-baseline values and the values at the “End of Treatment” visit (or the last value obtained under treatment).

Abnormal clinical laboratory results will be graded according to NCI CTCAE version 4.03, if applicable, as graded by the Central Lab (table reported in Section 15) and the grade will be presented in the by-patient data listing. Abnormal clinical laboratory test results of NCI CTCAE grade ≥ 3 will be listed within the main laboratory data listings.

The analysis of changes compared to baseline will be done as follows:

- A shift table, presenting the 2-way frequency tabulation for baseline and the worst post-treatment value according to the NCI CTCAE grade, will be provided for all clinical laboratory parameters where NCI CTCAE grading is available.

Results of serology (HIV, HBV, HCV) examination at screening will be summarized for the ITT set and will be provided together with the baseline characteristics in the analysis.

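### SAP Section 15 grades calcium with cut-offs that fit ionised calcium, but neither document says which calcium is measured; if it is total serum calcium, the calcium grades are wrong

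*SAP*

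**What the plan says.** SAP Section 15 has two calcium rows, given in mmol/L only.

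- **Calcium increased:** Grade 1 is ">ULN- 1.5 mmol/L", Grade 2 is ">1.5 -1.6 mmol/L", Grade 3 is ">1.6 -1.8 mmol/L", and Grade 4 is anything above 1.8 mmol/L.
- **Calcium decreased:** Grade 1 is "<LLN - 1.0 mmol/L", Grade 2 runs from below 1.0 to 0.9 mmol/L, Grade 3 is "<0.9 - 0.8 mmol/L", and Grade 4 is anything below 0.8 mmol/L.

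The row labels do not say total, albumin-corrected or ionised.

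Protocol 6.2.4 gives the chemistry panel as including "sodium, potassium, chloride, calcium, phosphorus, magnesium", with albumin and total protein further along the same list. Footnote M of the schedule of assessments (Protocol Appendix A and SAP 3.2) repeats the panel, and the schedule row calls it serum chemistry. Neither document gives a calcium reference range.

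SAP 9.4 applies CTCAE version 4.03 grades to abnormal results, "as graded by the Central Lab (table reported in Section 15". It uses the grades for a baseline-to-worst shift table and for marking results of Grade 3 or higher in the listings.

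**The concern.** A grading table works only if its cut-offs belong to the quantity that the laboratory reports. Here the cut-offs imply one form of calcium, and the panel, read in the ordinary way, suggests another. If the two differ, the calcium grades lose their meaning in both directions: a slight excess over the upper limit is reported as Grade 4, and a large deficit is reported as Grade 1. These grades are the only severity classification that the plan gives for laboratory calcium, so a reader of the clinical study report would take the shift table at face value.

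**Working it through.** **Inputs from the documents.** The cut-offs 1.5, 1.6 and 1.8 mmol/L (increase) and 1.0, 0.9 and 0.8 mmol/L (decrease), from SAP Section 15.

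**Inputs that are assumptions.** The documents give no calcium reference limits. I used a range for each fraction:

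- total serum calcium: lower limit (LLN) 2.0 to 2.25 mmol/L, upper limit (ULN) 2.5 to 2.75 mmol/L;
- ionised calcium: LLN 1.05 to 1.20 mmol/L, ULN 1.25 to 1.40 mmol/L.

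**Step 1: what the bands imply.** Grade 1 high runs from ULN to 1.5, so it contains values only if ULN < 1.5. Grade 1 low runs from LLN down to 1.0, so it contains values only if LLN > 1.0. Both hold only for a normal range inside 1.0 to 1.5 mmol/L. The assumed ionised limits meet both conditions. The assumed total limits fail the first by at least 2.5 − 1.5 = 1.0 mmol/L.

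**Step 2: is it a unit slip across the table?** Rows that print both units can be checked with mmol/L = mg/dL × 10 / molar mass:

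- glucose: 160 × 10 / 180.156 = 8.88 (printed 8.9);
- magnesium: 3.0 × 10 / 24.305 = 1.234 (printed 1.23);
- phosphorus: 2.5 × 10 / 30.974 = 0.807 (printed 0.8);
- uric acid: 10 × 10 / 168.11 = 0.595 (printed 0.59).

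The paired rows agree to the printed rounding or close to it, so the table has no general conversion error.

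**Step 3: high side, total calcium.** A value flagged high exceeds a ULN of at least 2.5, and 2.5 > 1.8, so it is Grade 4. Grades 1 to 3 would need a value that is both above ULN and no higher than 1.8. No such value exists.

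**Step 4: low side, total calcium.** Every value from LLN down to 1.0 is Grade 1. The fall below LLN that takes a value to the Grade 2 boundary is 1 − 1.0/LLN:

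| Assumed fraction | LLN (mmol/L) | Fall to the Grade 2 boundary |
|---|---|---|
| Total | 2.0 | 1 − 1.0/2.0 = 50.0% |
| Total | 2.1 | 1 − 1.0/2.1 = 52.4% |
| Total | 2.25 | 1 − 1.0/2.25 = 55.6% |
| Ionised | 1.05 | 1 − 1.0/1.05 = 4.8% |
| Ionised | 1.20 | 1 − 1.0/1.20 = 16.7% |

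For Grade 3 low, total calcium would have to fall below 0.9, that is by 1 − 0.9/2.0 = 55.0% to 1 − 0.9/2.25 = 60.0%. As an example, 1.4 mmol/L against an LLN of 2.1 is 1 − 1.4/2.1 = 33.3% below normal, and it is Grade 1.

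**Step 5: ionised calcium.** No part of the assumed normal interval falls in any graded band, and every band can be reached. The rows then work as printed.

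**The case against.** The strongest reply is that the documents never say total calcium. Serum chemistry names the sample, not the fraction. SAP 9.4 says that the central laboratory does the grading, so Section 15 may simply record that laboratory's scheme, and its cut-offs point to ionised calcium. This stands: the finding depends on the fraction measured, which is inferred from a routine panel with albumin and total protein. It does not close the matter. If ionised calcium is measured, both documents omit to say so. If total calcium is measured and the laboratory grades it with other limits, Section 15 misreports the method.

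A second reply is that little depends on these grades. SAP 9.4 also provides descriptive statistics, changes from baseline, and changes to the maximum and minimum post-baseline values, none of which use grades. Individual values are listed, investigators review every report (Protocol 6.2.4), and adverse event grades come from the treating physician (SAP 9.2). This also stands, and it limits the reach of the point.

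Three stronger readings are tempting, and the documents do not support them.

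- **Nearly all patients would be Grade 4.** A normal total calcium is numerically above 1.8 mmol/L, but SAP 9.4 grades abnormal results and Protocol 6.2.4 has the laboratory flag them. A value flagged normal need not be graded. The risk arises only if the bands are programmed without that flag.
- **Grade 2 or higher hypocalcaemia cannot appear.** It can, but only with total calcium below 1.0 mmol/L, about half of LLN or less.
- **The error undermines QT monitoring.** The close-monitoring sentence in Protocol 4.2.2.4 concerns patients on drugs that may alter electrolytes, and the electrolytes named there are potassium, phosphate and magnesium, not calcium. Section 15 governs reporting and not patient monitoring.

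**Conclusion.** The point holds in conditional form. What the table itself shows is that the calcium bands require a normal range inside 1.0 to 1.5 mmol/L and that the analyte is not identified. That this range fits ionised and not total calcium rests on the assumed reference limits, and the result is the same at every combination tried. If total calcium is measured and graded as printed, the calcium shift table and the Grade 3 or higher flags are wrong: every high value is Grade 4, and low values stay at Grade 1 until a fall of roughly half. The effect is confined to those calcium outputs. Descriptive summaries, raw listings, investigator-graded adverse events, overall survival and all other efficacy analyses are not affected.

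**What to change.** Ask the central laboratory which calcium fraction it reports and which limits it used for grading.

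- **If total calcium:** replace the two Section 15 rows with the albumin-corrected serum-calcium limits of CTCAE version 4.03, which the SAP already names. Take them from that source, because the documents do not print them. Re-run the calcium grades, the shift table and the Grade 3 or higher listing. Albumin is already in the panel, so no new samples are needed.
- **If ionised calcium:** keep the rows, and label the analyte as ionised in Protocol 6.2.4 and in SAP 9.4 and Section 15.

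The cost is one query to the laboratory, an edit to two table rows or their labels and, at most, a re-run of one parameter's grading.
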